8.1.3. Change and Percent Change from Baseline

For any measure, the *change* and the *percent change from baseline* at a post-baseline visit will be derived as:

- Change from Baseline = (Score at the Post-Baseline Visit) (Baseline Score)
- Percent Change from Baseline = $100 \times$ Change / (Baseline Score)

8.1.4. Change after Injection

For any measure assessed pre and post administration of an IP at injection visits, the *change after injection* at an injection visit will be derived as:

• Change after injection = (Post-Administration score) – (Pre-Administration score)

If multiple pre-injection or post-injection scores were collected at an injection visit, then the score closest to the injection time will be used to derived the change after injection variable.

8.1.5. Efficacy Measures

Table 2 lists all the efficacy measures that were evaluated in LUMINA study.

Efficacy measure	Note
Vitreous haze (VH)	VH was graded using the modified SUN scale as 0, 0.5+, 1+, 1.5+, 2+, 3+, or 4+. A decrease in VH score indicates improvement in the vitreous inflammation.
Overall prednisone-equivalent dose	The overall prednisone-equivalent dose (mg/day) of all eligible systemic corticosteroids in each day
Best-corrected visual acuity (BCVA)	BCVA measures the acuteness or clearness of best- corrected vision, with a range of [0, 110] in ETDRS letters. An increase in BCVA indicates improvement in the best-corrected vision. A 5-letter difference in visual acuity is equivalent to one Snellen line. A BCVA score of 85 ETDRS letters is equivalent to 20/20 vision, which is considered normal vision.
Central Subfield Thickness (CST)	For each eye, the CST was measured using Optical Coherence Tomography (OCT). OCT was performed using reading center certified photographers, equipment, and standardized protocols.
NEI VFQ-25: Composite score and 12 subscales (General Health, General Vision, Ocular Pain, Near Activities, Distance Activities, Vision-Specific Social Functioning, Vision-Specific Mental Health, Vision- Specific Role Difficulties, Vision-Specific Dependency, Driving, Color Vision, Peripheral Vision)	As shown in Appendix A, each NEI VFQ item was recorded to a 0-100 scale. The composite score and subscales will be derived based on the recorded items. An increase in the NEI VFQ-25 composite score or subscale indicates improvement in certain visual function. Note that the 39-item NEI VFQ (VFQ-25 + optional items) conducted at the US sites will be used to derive the VFQ-25 composite score and subscales (double- check).

Table 2:Efficacy Measures

8.1.6. Rescue Therapy

Rescue therapy is defined as any treatment that would have a therapeutic effect on NIU-PS, other than intravitreal DE-109.

- Systemic corticosteroid therapy (except during the tapering window)
- New systemic treatment with an immunosuppressant agent
- Increase in dose of ongoing therapy with methotrexate, azathioprine, or mycophenolate mofetil (or an equivalent drug, e.g., mycophenolic acid)
- Anti-vascular endothelial growth factor therapy (anti-VEGF)
- New or increased dose/frequency of topical ocular corticosteroid to the study eye
- New or increased dose/frequency of topical ocular nonsteroidal anti-inflammatory agent to the study eye
- Ocular or periocular corticosteroid injection to the study eye

- Use of difluprednate ophthalmic emulsion eye drops in the study eye
- Vitrectomy in the study eye

Other protocol-allowed or specified medications that are not considered rescue therapy are listed as follows:

- Investigational product (DE-109, Sham, Dummy).
- Oral corticosteroids administered in accordance with the protocol-specified tapering schedule (refer to Protocol Section 6.5.3).
- Ongoing stable dose/frequency of corticosteroid eye drops is permitted (exception of difluprednate), non-steroidal anti-inflammatory eye drops, methotrexate, azathioprine, or mycophenolate mofetil are allowed by the protocol.
- The protocol-specified administration of prednisolone acetate eye drops following each IP administration.

Rescue therapies will be performed when worsening of uveitis in the study eye is observed satisfying one or more of the following three rescue criteria:

- 1. Worsening of uveitis in the study eye as indicated by at lease a 2-step increase in VH score (i.e., 0 to ≥2+, 0.5+ to ≥3+, 1+ to ≥3+, 1.5+ to ≥4+, or 2+ to ≥4+) as compared to the baseline (Day 1) VH score or the best achieved VH score post baseline.
- Severe deterioration of vision in the study eye due to worsening of uveitis that is indicated by at least doubling of the visual angle (BCVA loss of 3 or more lines [≥15 ETDRS letters]) as compared to baseline (Day 1) BCVA.
- 3. New or worsening retinal or choroidal uveitic lesion(s) in the study eye determined by clinical examination, as compared to baseline.

These three above criteria are generally referred to as protocol-specified rescue criteria.

When subjects got rescued when deemed medically necessary even if none of the protocolspecified rescue criteria were satisfied, all of the reasons will be pooled together and referred to as *Other* rescue criterion. Further breakdown of reasons under the "Other" category might be performed if deemed necessary.

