6.5.3. Tapering of Systemic Corticosteroid Therapy

For study eligibility, subjects receiving systemic (oral) corticosteroid therapy will be required to titrate the dose as needed such that they remain on a stable oral prednisone-equivalent dose between \geq 15 mg/day and \leq 40 mg/day that has remained stable for at least 1 week (7 days) prior to and including Day 1. The Intent-to-Taper population is defined as those subjects who are receiving oral corticosteroid therapy on Day 1. Starting on Day 1, the corticosteroid dose of these subjects should be reduced weekly over a maximum of 8 weeks to discontinuation (0 mg/day) according to the following tapering schedule:

- Reduce by 10 mg weekly until a dose of 20 mg is reached
- Then reduce by 5 mg weekly until a dose of 10 mg is reached
- Then reduce by 2.5 mg weekly until reaching 0 mg

If the above-suggested tapering scheme needs to be amended significantly, the investigator must consult with the study medical monitor.

6.5.4. Continuation of Stable Doses of Topical Ocular Corticosteroid Medication, Topical Ocular Non-Steroidal Anti-Inflammatory Medication, or Selected Immunosuppressants

Use of difluprednate ophthalmic emulsion eye drops in the study eye(s) within 7 days prior to Day 1 is prohibited. Difluprednate ophthalmic emulsion eye drops are prohibited throughout the duration of the study. Subjects being treated with other topical corticosteroid eye drops or with topical non-steroidal anti-inflammatory eye drops must have received stable dosing (same medication type and frequency of use) for at least 7 days prior to Day 1 in order to be eligible for enrollment in the study. These subjects will be allowed to continue the therapy at stable dosing during the study (same medication type and frequency of use). Decreases and termination of dose are allowed during the study. Similarly, subjects being treated with one of the following: methotrexate, azathioprine, or mycophenolate mofetil must have received a stable dose for at least 30 days prior to Day 1 with the expectation that the dose will remain stable until the end of the trial. These subjects should continue the therapy at a stable dose during the study.

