6.5.6. Rescue Therapy

Rescue therapy is defined as any treatment that would have a therapeutic effect on NIU-PS, other than intravitreal DE-109. Other protocol-allowed or specified medications that are not considered rescue therapy are listed in Section 6.5.7.

The following are examples of rescue therapies:

- Systemic corticosteroid therapy (except as described in Section 6.5.7)
- New systemic treatment with an immunosuppressant agent
- Increase in dose of ongoing therapy with methotrexate, azathioprine, or mycophenolate mofetil (see inclusion criteria Section 5.1, #6)
- Anti-vascular endothelial growth factor therapy (anti-VEGF)
- New or increased dose/frequency of topical ocular corticosteroid to the study eye (see inclusion criteria Section 5.1, #8)
- New or increased dose/frequency of topical ocular nonsteroidal anti-inflammatory agent to the study eye (see inclusion criteria Section 5.1, #8)
- Ocular or periocular corticosteroid injection to the study eye
- Use of difluprednate ophthalmic emulsion eye drops in the study eye
- Vitrectomy in the study eye

Because rescue therapies such as those noted above may or will have a therapeutic effect on the uveitis in the posterior segment, they are prohibited unless worsening of uveitis in the study eye is observed satisfying one or more of the following three rescue criteria:

- 1. Worsening of uveitis in the study eye as indicated by at least a 2-step increase in VH score (i.e., 0 to $\geq 2+$, 0.5+ to $\geq 3+$, 1+ to $\geq 3+$, 1.5+ to $\geq 4+$, or 2+ to $\geq 4+$) as compared to the baseline (Day 1) VH score or the best achieved VH score post baseline.
- Severe deterioration of vision in the study eye due to worsening of uveitis that is indicated by at least doubling of the visual angle (BCVA loss of 3 or more lines [≥15 ETDRS letters]) as compared to baseline (Day 1) BCVA.
- 3. New or worsening retinal or choroidal uveitic lesion(s) in the study eye determined by clinical examination, as compared to baseline.

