6.5.7. Protocol-Allowed or Specified Medications not Considered Rescue Therapy

Protocol-allowed or specified medications NOT considered rescue therapy are as follows:

- Investigational product (DE-109, Sham, Dummy).
- Oral corticosteroids administered in accordance with the protocol-specified tapering schedule (Section 6.5.3).
- Ongoing stable dose/frequency of corticosteroid eye drops is permitted, non-steroidal anti-inflammatory eye drops, methotrexate, azathioprine, or mycophenolate mofetil, as allowed by the protocol.
- The protocol-specified administration of prednisolone acetate eye drops following each IP administration.

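### SAP 8.1.6 states two different exemptions for systemic corticosteroid during the taper, so the rescue flag is not uniquely defined for some Intent-to-Taper eyes

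*SAP*

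**What the plan says.** SAP Section 8.1.6 deals with systemic corticosteroid in three places.

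- General definition: "Rescue therapy is defined as any treatment that would have a therapeutic effect on NIU-PS, other than intravitreal DE-109".
- First bullet under that definition: "Systemic corticosteroid therapy (except during the tapering window". The SAP does not define the window.
- List of medications that are not rescue, in the same section: "Oral corticosteroids administered in accordance with the protocol-specified tapering schedule (refer to Protocol Section 6.5.3".

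Protocol Section 6.5.6 words the corresponding bullet differently: "Systemic corticosteroid therapy (except as described in Section 6.5.7". The exemption it points to, in Section 6.5.7, is "Oral corticosteroids administered in accordance with the protocol-specified tapering schedule (Section 6.5.3".

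Protocol Section 6.5.3 says that the dose "should be reduced weekly over a maximum of 8 weeks to discontinuation". It also leaves room for change: "If the above-suggested tapering scheme needs to be amended significantly, the investigator must consult with the study medical monitor". Neither document says whether a taper amended in this way still counts as following the schedule.

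**The concern.** The SAP bullet asks when the steroid was given. The SAP not-rescue list and the protocol ask whether it was oral and on schedule. For a subject who tapers as written, the answers agree. They part when a dose is raised, restarted or given by a non-oral route during the taper weeks.

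Rescue status feeds the composite score (two of the three key secondary endpoints), use of rescue, tapering success, VH response at Month 6 and in the open-label period, and the data kept in the repeated-measures models. For some eyes it also feeds the primary endpoint and VH 0 at Month 3. Two programmers working from Section 8.1.6 could derive different flags from the same records, and the choice could be settled after the data have been seen.

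**Working it through.** **1. The two rules side by side**

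| | SAP 8.1.6 rescue bullet | SAP 8.1.6 not-rescue list; Protocol 6.5.6 and 6.5.7 |
|---|---|---|
| Basis of exemption | Time inside the window | Conformity with the Section 6.5.3 taper |
| Route | Any systemic route | Oral only |
| Off-schedule increase inside the window | Exempt | Not exempt |

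**2. Length of the window**

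Read as the 8-week maximum in Protocol 6.5.3, the window ends by Day 1 + 56 = Day 57. With *k* weekly cuts, 0 mg/day is reached on Day 1 + 7(*k* − 1) if the first cut is on Day 1, or on Day 1 + 7*k* if it comes a week later.

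- 40 mg/day start: 40-30-20-15-10-7.5-5-2.5-0, *k* = 8, so Day 50 or Day 57.
- 15 mg/day start: 15-10-7.5-5-2.5-0, *k* = 5, so Day 29 or Day 36. This leaves 57 − 29 = 28 or 57 − 36 = 21 days of window after the scheduled end of the taper.

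The window closes before Month 3 (Day 90 ± 3) and Month 5 (Day 150 ± 3).

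**3. Which courses are classified differently**

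The doses below are invented to test the classification and imply nothing about management.

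- *Early increase, 15 mg/day starter, first cut on Day 1:* 10 mg on Day 1, 7.5 on Day 8, raised to 15 on Day 15, then 10 on Day 22, 7.5 on Day 29, 5 on Day 36, 2.5 on Day 43 and 0 on Day 50. The course ends before Day 57, so the bullet exempts all of it. The other wording does not exempt the increase.
- *Late increase, subject on 5 mg raised to 7.5 mg on Day 43:* 5 on Day 50, 2.5 on Day 57, 0 on Day 64. Steroid is taken after Day 57, so the bullet itself makes it rescue and the two rules agree.

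The conflict is therefore confined to courses that start and finish inside the window, unless the undefined window is read as longer.

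**4. Consequence for the early-increase eye, with no protocol rescue criterion met**

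| Analysis (SAP section) | SAP bullet | Other wording |
|---|---|---|
| VH 0 at Months 3 and 5 (2.2.1, 5.2.1, 8.2.1) | Observed VH used | Rescue for other reasons: later VH censored and imputed |
| Composite at Months 3 and 5 (2.2.3) | Can score 3, 2 or 1 | Cannot score 1 to 3; gets 0, or −1 if the rescue is attributed to worsening |
| Use of rescue (2.3.3) | No | Yes |
| Tapering success (2.3.3, 8.1.8) | Possible, if at 0 mg/day with VH 0 at the visit | Failure |
| VH response at Month 6 and later (8.1.7) | Decided by VH | Non-responder |
| VH and BCVA MMRM (8.2.4.2); GEE (8.2.2) | Data kept | Data after start of rescue excluded |

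If the eye does meet a protocol rescue criterion, SAP 5.2.1 and 8.2.1 make it a VH non-responder whether or not it was treated. The two rules then agree for the Month 3 and Month 5 VH responses.

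**5. Size**

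The only figure in the plan that gives a scale is the sample size (SAP 3.3): 30% against 12%, two-sided 0.05, 80% power.

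n = [1.960 × √(2 × 0.21 × 0.79) + 0.842 × √(0.30 × 0.70 + 0.12 × 0.88)]² / 0.18² = 79.2, so 80 per arm. Power at 80 per arm is 80.4%. The stated figure reproduces, and this point does not change it.

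The effect of the conflict needs the number of Intent-to-Taper eyes and the frequency of off-schedule courses. Neither is given. As an illustration under assumed counts only, with one eye per subject:

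| Net extra primary responders (of 80) | Power |
|---|---|
| None | 80.4% |
| One on sham | 73.4% |
| Two on sham | 65.7% |
| One on DE-109 | 84.7% |
| One on each arm | 78.7% |

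These are not estimates. They show that the direction depends on which arm the reclassified eyes fall in.

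**The case against.** The strongest reply is that the SAP does not adopt a wider exemption at all. Section 8.1.6 opens with a broad definition of rescue, and its not-rescue list repeats the protocol's rule with a reference to Protocol 6.5.3. The bullet may simply be shorthand for that list. This has force: a reader might infer that the SAP exempts all steroid given during the taper, and the section as a whole does not support that. It still leaves two stated rules, an undefined window, and no statement of which rule governs the flag.

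A reader might also infer that a re-escalated eye is turned from a failure into a success on the primary endpoint. The documents do not support that either. Eyes meeting a rescue criterion fail under both wordings. The remaining eyes move between observed and imputed VH, and an imputed eye can be a responder. An eye with observed VH above 0 is a non-responder under the bullet but could be imputed as a responder under the other wording.

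For the same reason, it does not follow that each 1% of sham eyes affected removes one point of the planned 18-point difference (30% − 12%), or that sham is mainly credited. More re-escalation on sham is plausible, but nothing in the documents shows it.

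Finally, tapering success still requires 0 mg/day and VH 0 at a visit after the window has closed, and late increases usually run past the window. Both points stand and narrow the set of affected eyes.

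**Conclusion.** The contradiction is real, both within SAP 8.1.6 and between it and Protocol 6.5.6 and 6.5.7. It matters for off-schedule or non-oral systemic corticosteroid courses in Intent-to-Taper subjects that fall wholly inside the window without a protocol rescue criterion being met. For those eyes the wording chosen decides the flag. The clearest consequences are for the composite, use-of-rescue and tapering endpoints. For VH 0 at Months 3 and 5 the difference is observed against censored and imputed data.

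Neither the size nor the sign of the net effect can be established from the documents. The conclusion assumes that the window means the 8-week maximum taper; a longer reading would widen the set of eyes affected.

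**What to change.** Before unmasking, reconcile the SAP 8.1.6 rescue bullet with the SAP's own not-rescue list and with Protocol 6.5.3, 6.5.6 and 6.5.7, so that a single definition drives the analysis rescue flag. One way is to have the bullet cross-refer to Protocol 6.5.7, as Protocol 6.5.6 already does. If a time window is kept, define it.

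In the same place, state how a taper amended after consultation with the medical monitor is flagged. A blanket rule that any dose above the previous step is rescue would go beyond the documents, because Protocol 6.5.3 allows amendment.

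Derive the flag from the route, dose and start and stop dates already collected under Protocol 6.5.1 and 6.5.6. The daily prednisone-equivalent dose in SAP Table 2 may not be enough by itself, since it covers eligible systemic corticosteroids and the table does not say which those are.

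The cost is one SAP phrase and a documented derivation rule, with no new data collection. This concerns the analysis flag only; no clinical rule is proposed.

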8.1.7. Response Endpoint and Response Rate

Three VH response endpoints will be evaluate at Month 3, Month 5, Month 6, and at each visit after Month 6 in this study. VH response endpoints are defined as follows:

- VH 0 response: having a VH score of 0 (modified SUN scale). Study eyes which met this criterion are called *VH 0 responders*.
- VH 0 response: having a VH score of 0 or 0.5+ (modified SUN scale). Study eyes which met this criterion are called *VH* 0 or 0.5+ responders.
- VH 0 response: having a VH score of 0 or a decrease (improvement0 of at least 2 units from baseline in VH score (modified SUN scale). Study eyes which met this criterion are called *VH* 0 or 2-unit responders.

For response endpoints at Month 6 and at visits of the Open-Label analysis period, subjects who were rescued before the visit when the endpoint is evaluated will be treated as non-responders. The response rate will be estimated as the proportion of responders in the corresponding treatment group.

8.1.8. Intent-to-Taper Subject and Corticosteroid Tapering Success

Subjects who were taking systemic (oral) corticosteroid(s) at baseline (Day 1) with the overall prednisone-equivalent dose between 15 mg/day and 40 mg/day are called *Intent-to-Taper* subjects. An Intent-to-Taper study eye will be considered a corticosteroid taper success if the corresponding subject's overall prednisone-equivalent dose was tapered off to 0 mg/day and the study eye achieved VH score of 0 at Month 5. Intent-to-Taper study eyes which were rescued before Month 5 will be treated as corticosteroid tapering failures.

The *tapering success rate* will be estimated as the proportion of corticosteroid tapering successes among Intent-to-Taper study eyes in the corresponding treatment group.

8.1.9. Best-corrected Visual Acuity Response

The BCVA response endpoint is defined as a study eye having an increase (improvement) of at least 15 ETDRS letters (i.e., 3 lines) at Month 5. The BCVA response endpoint will be summarized for Vision 20/40 or Worse Population.

8.1.10. Central Subfield Thickness Response

In the study, subjects with the CST in the study eye \geq 300 microns at baseline (Day 1) are called macular edema subjects. CST 50-micron response is defined for macular edema subjects as having a decrease (improvement) of at least 50 microns in CST at Month 5.

8.2. Analyses of Primary Endpoint and Secondary Endpoints

Unless specified otherwise, efficacy analyses will be performed on the study eye, based on the FAS, and data on fellow eye will not be used.

8.2.1. Primary Analyses

The primary efficacy endpoint, VH 0 response, is defined as having a VH score of 0 at Month 5 (modified SUN scale). For the primary endpoint, the VH 0 response rate will be evaluated in accordance with the following null (versus alternative) hypothesis:

$$H_0: \pi_{sham} = \pi_{440}$$
versus

$$H_A: \pi_{sham} \neq \pi_{440}$$

where π_{sham} and π_{440} denote the response rate for sham and 440 µg DE-109, respectively.

The Cochran-Mantel-Haenszel (CMH) test with Row Mean Scores statistic (Yu et al., 2020), stratified by pooled strata based on the number of enrolled eyes from a subject (one eye or two eyes), baseline systemic (oral) corticosteroid use (yes or no), and region (US or non-US). Such pooling is needed to avoid the situation where subjects in too small strata might all have the same responses (either success or failure); hence, do not contribute to the test. To guarantee that

a pooled stratum has at least one success and one failure, the pooling algorithm will be performed as follows:

- Determine the number of subjects in each stratum, defined by crossing the number of enrolled eyes, baseline systemic corticosteroid use, and region.
- Within each combination of number of enrolled eyes and region, if one or both strata, stratified by corticosteroid use, have less than 25 subjects, then those strata will be pooled.
- Within each stratification factor level based on number of enrolled eyes, if at least one of (pooled/unpooled) strata have less than 25 subjects, then those strata will be pooled together.

The pooling algorithm will be performed based on the available data prior to the unmasking of the randomization. At the interim analysis, only number of enrolled eyes will be used as the stratification factor.

Study eyes will be treated as non-responders if they meet at least one of the following criteria:

- 1. A study eye is rescued due to the protocol-specified worsening of uveitis (Section 8.1.6)
- 2. A subject discontinued from the study due to lack of efficacy or adverse events
- 3. A study eye meets the protocol-specified worsening of uveitis rescue criteria (Section 8.1.6) regardless whether the eye received any rescue therapies

Study eyes which were rescued due to worsening of uveitis specified under previous protocol version but did not meet the rescue criteria under the current version will be treated as rescued due to other reason and censored the data after being rescued. The multiple imputation-based approach will be applied to impute missing VH score data of study eyes which were not rescued and treated as non-responders. The VH 0 response status will then be determined based on the observed or imputed VH score.

For missing VH score due to any other reasons other than protocol-specified worsening of uveitis, the multiple imputation approach will be applied as follows:

- 1. Use Markov chain Monte Carlo (MCMC) to create monotone missingness first with VH score on the logarithm scale. Then obtain standard multiple imputations under MAR assumptions for missing VH scores using monotone regression on the logarithm scale. The imputed values will be then converted into an eligible VH score based on the absolute distance. The missing data are filled in and 50 complete datasets are created. The seed that will be used in the SAS program is 135711.
- 2. Each of 50 complete datasets will then be analyzed separately. The CMH test statistic, response rate for each treatment group, and the rate difference will be calculated for each complete sets.
- 3. The final CMH test statistic, obtained from each complete dataset, will be transformed using Wilson-Hilferty transformation and combined for inference purposes (O'Kelly et al., 2014). Rates and rate differences will also be combined without any transformations.

The Mantel-Haenszel weighted response rate (%) of each treatment group, the Mantel-Haenszel weighted rate difference, the corresponding asymptotic 95% confidence interval (CI) and the CMH's p-value will be reported.

The main part of the SAS code for the specified CMH test procedure and the multiple imputation are provided in Appendix C, respectively.

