2.2.3. Composite estimands

Mean composite score in DE-109 440 μ g group vs. Sham group at Month 3 and at Month 5 in all study eyes that received at least one dose of study treatment. Each study eye will be assigned one of the following scores:

• Score = 3 if a study eye achieved VH score of 0 at the specified visit without taking any rescue therapies that could affect VH score prior to the specified visit

- Score = 2 if a study eye had at least improved by 2 units in VH (compared to baseline) at the specified visit without taking any rescue therapies that could affect VH score prior to the specified visit
- Score = 1 if a study eye achieved VH score of 0.5+ at the specified visit without taking any rescue therapies that could affect VH score prior to the specified visit
- Score = -1 if a study eye got rescued due to worsening of uveitis or discontinued from the study due to lack of efficacy or due to adverse events prior to the specified visit
- Score = 0 if otherwise

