3.3. Sample Size Planning

Assuming a 30% VH 0 response rate for DE-109 440 μ g group and a 12% response rate for the sham treatment group, 160 subjects (80 subjects per arm) is required to achieve 80% power to detect such a difference in response rate between the DE-109 440 μ g group and the sham treatment group using the Pearson's Chi-square test (two-sided, $\alpha = 0.05$). Including approximately 40 subjects in the dummy arm, a total of approximately 200 subjects with active NIU-PS will be randomized in a 2:2:1 ratio to DE-109 440 μ g, sham, and dummy arms. Because some subjects will contribute two study eyes to this study, the planned sample size of 80 subjects

in both the test (DE-109 440 $\mu g)$ and control (sham procedure) arms will achieve more than 80% power.

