5.4. Multiple Comparisons / Multiplicity

To control the overall Type I error rate associated with the multiple comparisons on the primary and the key secondary endpoints at the 0.05 level (two-sided), the following hierarchical testing strategy will be employed:

- A. Conduct the statistical testing for the primary comparison between DE-109 440 μg and Sham treatment arm on the primary endpoint (VH 0 response) at the significance level of 0.05 (two-sided)
- B. If the result of the primary comparison on the primary endpoint is positive (i.e., *p*-value < 0.05), then conduct the statistical testing for the primary comparison between DE-109 440 μg and Sham treatment arm on the following key secondary endpoints in a hierarchical fashion:
 - 1. Mean composite score at Month 5
 - 2. VH 0 response at Month 3
 - 3. Mean composite score at Month 3

The primary comparison on the $(i+1)^{th}$ key secondary endpoint will be performed inferentially ONLY IF the result of the primary comparison in the ith key secondary endpoint is positive, where i = 1 or 2.

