8.2.2. Sensitivity Analyses

The following sensitivity analyses will be performed to assess the robustness of the results from the primary analysis:

- The primary analysis will be repeated on the PP Population.
- The CHM test stratified by the same pooled strata as in the primary analysis will be performed on the FAS population the missing data due to other reasons handled using the Last-Observation-Carried-Forward (LOCF) approach. Subjects who were rescued due to the protocol-specified worsening of uveitis or discontinued from the study due to lack of efficacy or adverse events prior to Month 5 will be treated as non-responders.
- Treatment policy strategy: The CHM test stratified by the same pooled strata as in the primary analysis will be performed on the FAS population regardless whether study eyes get rescued. The missing VH score will be imputed using multiple-imputation approach in the similar manner as described in Section 8.2.1.
- A generalized estimating equation (GEE) method will be used on observed cases up to Month 6 using identity link function. The GEE might be applied on the imputed data (via the same imputation approach as in primary analysis) if there are considerable large amount of missingness. The model will include pooled geographic region (US vs non-US), baseline VH score of the study eye (1.5+, 2+, '3+ or 4+'), treatment, visit, and treatment-by-visit as explanatory variables. An unstructured (UN) correlation structure will be used to model the correlation of the responses from subjects. For subjects rescued before Month 6, all VH scores of study eye collected after the start date of rescue therapy will be excluded from the analysis.
- If the UN correlation structure fails to converge, then an exchangeable (EXCH) correlation structure will be used to model the correlation. If the EXCH model fails to converge, then the independent model will be used.
- Multiple imputation with tipping point analysis will be performed to assess the impact of missing data on the primary analysis results. The following steps will be performed to generate different possible imputation scenarios:

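### The primary VH 0 test and the composite tests leave out baseline vitreous haze; this may forgo up to about 4 points of power, but it biases nothing.

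*SAP*

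**What the plan says.** SAP 8.2.1 makes the primary test a CMH test "stratified by pooled strata based on the number of enrolled eyes from a subject (one eye or two eyes"), baseline oral corticosteroid use and region. Strata with fewer than 25 subjects are pooled. Protocol 9.2 and Table 8 name the same test and factors. SAP 8.2.3 analyses the composite scores and Month 3 VH 0 in the same way.

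Randomisation uses those three factors and not baseline VH (Protocol 6.3, SAP 3.2). Baseline VH is known for every study eye, because a Day 1 score of at least 1.5+ is an entry criterion (Protocol 5.1).

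Other analyses in the SAP do use it:
- The GEE sensitivity model for VH 0 includes "baseline VH score of the study eye (1.5+, 2+, '3+ or 4"+) (SAP 8.2.2).
- The MMRM for change in VH has it as a covariate, and the MMRM for BCVA as a factor. The VFQ-25 ANCOVA also has it as a factor (SAP 8.2.4.2).
- It defines a descriptive subgroup (SAP 8.3).

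The composite refers to baseline directly: "Score = 2 if a study eye had at least improved by 2 units in VH (compared to baseline") (SAP 2.2.3).

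**The concern.** The primary endpoint is reaching VH 0 from a start anywhere between 1.5+ and 4+, so an eye's starting level may well predict whether it gets there. Adjusting for a prognostic baseline variable usually sharpens a treatment comparison at little cost. The SAP accepts that reasoning for supportive models and gives no reason for leaving the variable out of the test that decides the trial.

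For the composite the dependence is partly structural, since the scores open to an eye depend on where it started.

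The stake is modest but real. The trial is sized at 80% power with little to spare, and the Month 5 composite gates the two remaining key secondary endpoints (SAP 5.4).

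**Working it through.** **Planned sample size.** Inputs from SAP 3.3: 30% versus 12%, two-sided alpha 0.05, 80% power, Pearson chi-square.

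n per arm = [z(α/2)·√(2·p̄·q̄) + z(β)·√(p₁q₁ + p₀q₀)]² / (p₁ − p₀)², with p̄ = 0.21.

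= [1.96·√0.3318 + 0.8416·√0.3156]² / 0.18² = (1.129 + 0.473)² / 0.0324 = 79.2, so 80 per arm. Power at 80 per arm is 80.4%. The plan's figure, "160 subjects (80 subjects per arm) is required to achieve 80% power to" detect this difference, reproduces.

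**Which composite scores are reachable.** From 1.5+ a 2-unit fall is impossible. From 2+ it lands on 0, which scores 3. Score 2 therefore exists only for baselines of 3+ or 4+.

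**Rough gain from adjustment.** If baseline VH explains a share R² of the outcome variance, effective N = 160/(1 − R²):
- R² 2%: 160/0.98 = 163.3, power 81.2%
- R² 5%: 160/0.95 = 168.4, power 82.4%
- R² 10%: 160/0.90 = 177.8, power 84.4%

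**Simulated gain, one eye per subject.** The documents give neither the baseline VH mix nor its link with response. Assumed: shares of 35/45/20% for 1.5+, 2+ and 3+ or 4+, and odds of VH 0 divided by a fixed odds ratio (OR) at each step up. At OR 2 this means DE-109 rates of 42/27/16% and sham rates of 18/10/5%; at OR 4, 53/22/7% and 24/7/2%. Overall rates stay at 30% and 12%. The estimator was a least-squares risk difference with robust standard errors and main effects for eyes, steroid use and region (25%, 35% and 50% of subjects, unrelated to outcome). There were 20,000 trials per scenario, so the Monte Carlo standard error of one power figure is √(0.8·0.2/20,000) = 0.28 points. Both analyses used the same simulated trials.

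| OR per category | R² | Without baseline VH | With VH, linear score | With VH, three levels |
|---|---|---|---|---|
| 1 | 0% | 80.6% | 80.4% | 80.2% |
| 1.5 | 1.3% | 81.1% | 81.4% | 81.2% |
| 2 | 3.5% | 81.5% | 82.6% | 82.5% |
| 3 | 7.9% | 81.1% | 83.7% | 83.6% |
| 4 | 11.5% | 80.6% | 85.0% | 85.1% |

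Type I error was 4.9% to 5.5% with and without adjustment.

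**Simulated gain with second eyes.** With 25% of subjects contributing two eyes and subject-level clustering, power moved from 84.8% to 84.6% at OR 1, 85.3% to 86.6% at OR 2, 85.3% to 88.3% at OR 3 and 85.4% to 89.1% at OR 4. Type I error was 5.1% to 5.3%. The differences matter here; the absolute level depends on the assumed share of two-eye subjects and the correlation between eyes.

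**The alternative of a further CMH stratum.** Crossing three-level VH with eyes and region (4 to 12 strata, 40,000 trials) moved power from 80.5% to 78.5% at OR 1, 80.5% to 79.9% at OR 2, 80.7% to 82.0% at OR 3 and 80.8% to 83.7% at OR 4. Starting from all eight strata (8 to 24), it moved from 79.5% to 75.1%, 79.5% to 76.8%, 79.6% to 78.8% and 79.7% to 80.9%. These runs applied no pooling. A two-level VH stratum under the fewer-than-25 rule avoided the loss but gained only about 0 to 1 point.

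**The case against.** The plan's choice is defensible. Its strata are exactly the randomisation factors, and the Amendment 3 summary gives that as the reason. Omitting a non-stratified covariate leaves a randomised comparison unbiased and its type I error intact. All of this stands.

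A reader might infer that chance imbalance in baseline VH would corrupt the result. Such imbalance can move an estimate. With 80 per arm and 35% at 1.5+, the between-arm difference in that share has standard error √(2·0.35·0.65/80) = 7.5 points, so a gap of 10 points or more has about an 18% chance. At OR 2 to 3 it would shift the rate difference by about 1.4 to 2.2 points, against a planned 18. But the unadjusted test and interval already allow for this, so it is a loss of precision and not a bias.

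The benefit also rests on an assumed gradient and is close to nil if that gradient is weak. This stands, and it limits the claim.

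The SAP is not silent on baseline VH: the GEE, the subgroup display and the baseline table (SAP 7.2) would all show an imbalance. The GEE is only a partial substitute. By default it runs on observed cases, it drops scores after rescue where the primary analysis counts protocol-specified rescue as non-response, and it does not carry the primary p-value.

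Two practical objections remain. Baseline VH belongs to the eye, while the strata count subjects; a per-eye covariate with clustering by subject deals with that. Responders are few: 80·0.30 + 80·0.12 = 33.6 expected in 160 subjects, counting one eye each. That is thin for a logistic model with many stratum terms, so the working model must stay small.

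**Conclusion.** The omission is real for the primary test and the composite tests, and it is a matter of efficiency only. Under the assumptions above, covariate adjustment is worth about 0 points of power at an OR per category of 1 to 1.5, +1 at 2, +3 at 3 and +4 at 4. It costs at most about 0.4 points if baseline VH is unrelated to response.

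A reader might go further and conclude that the trial is underpowered or that a known amount of power is being lost. The documents support neither. The planned 160 subjects reproduce, and nothing in the protocol or SAP gives the baseline VH mix or its relation to VH 0.

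The composite gain is not quantified. Its direction is not obvious either: a higher baseline opens score 2 but may make score 3 harder to reach.

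The simulations used a linear working model with complete data. A logistic standardised estimator combined over imputations was not simulated. The change is still worth making, because it is cheap before unmasking and loses its pre-specified standing afterwards.

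**What to change.** Before unmasking, pre-specify the following:
- **Primary endpoint and Month 3 VH 0:** a covariate-adjusted (standardised) rate difference from a working model with arm, the pooled randomisation strata and each eye's own baseline VH (1.5+, 2+, 3+ or 4+), with robust standard errors clustered by subject. Name the working model in advance. If it is logistic, name the linear version as the fallback for non-convergence.
- **Composite at Months 5 and 3:** an adjusted mean difference with the same terms and clustering.
- **Imputation:** combine the estimate and its standard error by Rubin's rules, in place of the Wilson-Hilferty step used for the CMH statistic.
- **Current CMH:** keep it as a sensitivity analysis.

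Do not add baseline VH as a further CMH stratum. Without pooling that lost 0.6 to 4.4 points at OR 2 or below, and with pooling it gained little.

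The cost is one more model, revised text in SAP 8.2.1 and 8.2.3, and a matching edit to Protocol 9.2 and Table 8, since both fix the CMH as the confirmatory test. SAP 5.5.1 also needs a sentence on whether interim conditional power stays on the CMH statistic; it already stratifies differently from the final test. No new data are needed, and there is little or no gain if baseline VH proves weakly prognostic.
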